## 1. Glossary

OPAC	Odense pancreas center
ICH	International conference on harmonization
AP	Acute pancreatitis
SIRS	Systemic inflammatory response syndrome
PAMORAs	Peripherally acting $\mu$ -opioid receptor antagonists
SIBO	Small intestinal bacterial overgrowth
eGFR	Estimated glomerular filtration rate
CRF	Case report form
PASS	Pancreatitis activity scoring system
HbA1c	HemoglobinA1c
CRP	C-reactive protein
IL	Interleukin
TNF- $\alpha$	Tumor necrosis factor alpha
CD163	Cluster of differentiation 163
PaO 2	Partial pressure of oxygen in arterial blood
GSRS	Gastrointestinal symptom rating scale
SOP	Standard operating procedure
GCP	Good clinical practice
AE	Adverse event
AR	Adverse reaction
SAE	Serious adverse event
SAR	Serious adverse reaction
SUSAR	Suspected unexpected serious adverse reaction

mSV

Millisievert

### **3. Funding**

The study was conceived and initiated by [name] [name], Department of Gastroenterology & Hepatology, Aalborg University Hospital. It is economically supported by a free grant of 7.3 MIO DKK by the Novo Nordisk Foundation. This grant will be used to cover expenses related to equipment, medication and salary for study personnel. The Novo Nordisk Foundation does not have any specific rights related to publication of the results, and positive as well as negative and/or inconclusive results will be published in scientific journals. All data will be publicly available to anybody incl. the Novo Nordisk Foundation after publication. Various funds will be applied for, to cover any additional financial expenses. Alternatively, Mech-Sense, Aalborg University Hospital will cover the remaining expenses. The grant from the Novo Nordisk Foundation as well as potential grants from other funds are deposited in a project account at the Hospital, which principal investigator [name] is responsible for. Any excess amount will be refunded after the study has been concluded. The involved researchers conduct the trial of general scientific interest without personal financial gain and none of the researchers involved in this study have economical interest in the Novo Nordisk Foundation or other financial supporters of this study.

### **4. Roles and responsibilities**

The present clinical study will be conducted in compliance with this protocol, the guidelines of the World Medical Association Declaration of Helsinki in its revised edition (Fortaleza, Brazil, October 2013), the guidelines of International Conference on Harmonization (ICH) GCP (CPMP/ICH/135/95), and designated Standard Operating Procedures.

The study will be conducted at four referral centers for pancreatitis in Denmark, located at Aalborg, Odense, Bispebjerg and Hvidovre University Hospitals. Aalborg University Hospital will take leadership as main sponsor for the clinical trial and has the overall responsibility for the quality of the study. [name] [name] who is specialist in gastroenterology, will be principal investigator and overall study coordinator. He will lead the study together with Associate [name] [name] and other researchers at Centre for Pancreatic Diseases and Mech-Sense at Aalborg University Hospital. These will assist in design, write the protocol, handle all procedures with the regulatory authorities and be responsible for data management, data analysis as well as publications. They have a long track record on research in clinical and experimental pain research, pancreatitis, opioids, opioid antagonists, and imaging as well as a large network and major experience with leadership of multicenter studies.

[name] [name] at the Department of Radiology, Aalborg University Hospital, will supervise the analysis of all cross-sectional imaging studies together with senior researcher [name]. The imaging research group at Department of Radiology is an integrated part of Centre for Pancreatic Diseases and the interdisciplinary research group Mech-Sense.

Researchers at Hvidovre and Bispebjerg Hospitals will undertake the analysis of blood and urine samples. They have major experience in these analyses and have previously undertaken several studies in patients with acute pancreatitis (AP).

[name] [name]-student at Centre for Pancreatic Diseases, Aalborg University Hospital will be responsible for managing and overseeing the study. This will be supported by PhD-student [name], Mech-Sense. A Ph.D. student at Department of Radiology, Aalborg University Hospital (not yet appointed) will manage the advanced imaging analysis.

## 5. Time schedule

The study is expected to be initiated (first subject included) in December 2020 and concluded (last subject, last visit) by December 2023. A detailed overview is given in the diagram below.

	2020	2021-2022	2023
Submitting protocol			
Conducting studies			
Data analysis			
Writing and submitting articles			

## 6. Introduction

### 6.1. Background and rationale

Acute pancreatitis (AP) has an annual incidence rate of approximately 35 pr. 100.000 person years in Denmark and has become one of the most frequent gastrointestinal discharge diagnoses (1). AP is associated with an overall complication rate of about 20%, and despite improved treatment the mortality is still near 3%. Unfortunately, no targeted pharmacologic treatment exists, to effectively alter the disease course, and the initial management of AP is currently based on supportive therapy with intravenous fluid resuscitation and analgesics. In the later stages, treatment is directed against complications such as mono- or multiorgan failure and infections, especially infected pancreatic necrosis (2).

The early phase of AP is characterised by a localized pancreatic inflammatory process, which can progress to a systemic inflammatory response syndrome (SIRS), which may be associated with multiorgan dysfunction - and failure (3). In turn, a compensatory anti-inflammatory response, whereby the inflammation becomes controlled, counterbalances the inflammatory process. However, in some cases an inadequate control of this counterbalance may lead to further organ dysfunction, immune paresis and late complications - in particular infections.

Pain is the cardinal symptom of AP and induces release of endogenous opioids, which is further potentiated by exogenous administered opioids used for pain management (4). The increased opioid exposure leads to a number of harmful effects on the gastrointestinal organs and the immune system (see figure 1). This may further promote the inflammatory response and worsen the course of the disease (5).

[figure not shown]

Figure 1: The effects of opioids on the gastrointestinal organs and the immune system

About 20% of patients with AP will develop recurrent acute pancreatitis (RAP). The etiology of this entity can in most cases be related to continuation of toxic exposure (e.g. alcohol and/or smoking) or occult biliary stones, that have been overlooked or inadequately treated during the index attack of AP. However, the etiology of approximately 10-30 % of RAP cases, remains unexplained despite a thorough diagnostic work up (6). Currently no treatment is available for these patients and many patients will continue to suffer from repeated attacks of pancreatitis. A large proportion will ultimately progress to chronic pancreatitis with loss of exocrine and endocrine pancreatic function, chronic abdominal pain, and an increased risk for developing pancreatic cancer (6) with great cost for both the individual patient and society.

Peripherally acting  $\mu$ -opioid receptor antagonists (PAMORAs) have been developed for the treatment of opioid induced bowel dysfunction (7). This specific medication group may also have beneficial effects in patients with AP and RAP but has never been investigated for this indication. Hence, PAMORAs have been shown to potentiate immune responses (8) and increase survival in cancer patients partly due to counteracting the harmful effects of opioids on inflammation (9). Opioid administration induces paralysis of the small intestines by decreased and dyscoordination of gut motility, which may promote bacterial overgrowth (10). Opioids also seem to augment intestinal permeability due to damage of the tight junctions between mucosa cells (11). Together with small intestinal bacterial overgrowth (SIBO), translocation of

bacteria from the leaky gut to the peripancreatic tissues and the systemic circulation may be fatal in patients with AP. PAMORAs may ameliorate this by counteracting the above-mentioned effects of opioids on the intestines. As the medication also increases intestinal and pancreatic fluid production and has a relaxing effect on the sphincter of Oddi, the administration of PAMORAs are expected to enhance flow in the pancreatic duct system (10) resulting in increased washout of pathogenic substances during attacks of AP. Also, under normal circumstances, the tone in sphincter of Oddi and pancreatic secretion is partly controlled by endogenous opioids, and therefore prophylactic treatment with PAMORAs in patients with RAP may further support flow in the pancreatic duct system.

#### 6.1.1. Study medication

In this study, the effects of PAMORA on disease development and progression in patients with AP will be investigated. Patients with AP will be administered Methylnaltrexone (Relistor®) intravenously. This medication is defined as the investigational product. Relistor® is approved and sold on the Danish marked for treatment of opioid-induced constipation. This PAMORA have not previously been investigated in patients with pancreatitis. The dose regimes for this study will be according to label. Please see the Summary of Product Characteristics for further details. For detailed description of possible side effects, see section 11.2. We have previously shown, in patients with opioid-induced obstipation and healthy subjects, that opioid antagonism incl. PAMORA treatment increases gut motility, relaxes gastrointestinal sphincters, increases the intestinal water content and improves the immune response, without affecting analgesia (10,12–15). The affinity of PAMORAs to the  $\mu$ -opioid receptors is much stronger than opioid analgesics. Therefore, they as antagonists have the potential to counteract the harmful effects of opioids on the gut mucosa, bacterial translocation and inflammation despite the high levels of exogenous opioids present in patients with pancreatitis. PAMORAs do not cross the blood-brain barrier and consequently do not interfere with analgesia or other central effects of opioids (12).

We hypothesize that treatment with the PAMORA methylnaltrexone will antagonize the harmful effects of opioids without reducing analgesia in patients with AP and hence reduce disease severity and improve clinical outcomes. If successful, this sub-study will for the first time document the effects of a targeted pharmacotherapy in AP with the potential benefit of improved patient outcomes.

#### 6.2. Hypothesis

In patients admitted with AP, 5 days treatment with intravenous methylnaltrexone will reduce the **disease severity** compared to placebo.

### 6.3. Trial design

This study is an investigator-initiated, double-blind, placebo-controlled, parallel-group of fixed methylnaltrexone dose conducted at four referral centers for pancreatitis in Denmark. A group of **90 patients with AP** will be prospectively included and randomized to receive intravenous methylnaltrexone or matching placebo in a 1:1 ratio. Patients will be treated for 5 days during hospital admission.

## 7. Methods: participants, interventions, and outcomes

### 7.1. Study setting

The study will be conducted at four referral centers for pancreatitis in Denmark, located at Aalborg, Odense, Bispebjerg, and Hvidovre University Hospitals. These centers have comprehensive experience in diagnosing, treating, and conducting research on patients with pancreatitis.

### 7.2. Eligibility criteria

#### 7.2.1. Inclusion criteria

- Signed informed consent before any study specific procedures
- Able to read and understand Danish
- Male or female age between 18 and 85 years
- The researcher believes that the participant understands what the study entails, is capable of following instructions, can attend when needed, and is expected to complete the study
- The investigator will ensure that fertile female participants have a negative pregnancy test before treatment initiation and use contraception during the study period. The following methods of contraception, if properly used, are generally considered reliable: oral contraceptives, patch contraceptives, injection contraceptives, vaginal contraceptive ring, intrauterine device, surgical sterilization (bilateral tubal ligation), vasectomized partner, double barrier (condom and pessary), or sexual abstinence. Methods of contraception will be documented in the source documents
- Within the current hospital admission and prior to inclusion, the patient must fulfill at least two of the following criteria to establish a diagnosis of AP (according to the revised Atlanta criteria (20)): i) abdominal pain consistent with AP (acute onset of a persistent, severe, epigastric pain often radiating

to the back); ii) serum amylase activity at least three times greater than the upper limit of normal; and iii) characteristic findings of AP on diagnostic imaging

- Predicted moderate or severe AP based on the fulfillment of 2 or more SIRS criteria within the last 24 hours prior to inclusion (see figure 2)

#### 7.2.2. Exclusion criteria

- Definitive chronic pancreatitis according to the M-ANNHEIM criteria (21) -
- Known allergy towards study medication
- Known or suspected major obstruction or perforation of the intestines
- Toxic megacolon
- Known or suspected abdominal cancer (incl. intestine, pancreas and the biliary tree)
- Pre-existing renal insufficiency (defined as habitual estimated glomerular filtration rate (eGFR) below 45 ml/min/1,73m^2)
- End-stage renal impairment requiring dialysis prior to inclusion
- Severe pre-existing comorbidities (assessed by investigator upon inclusion)
- Severe non-pancreaticobiliary infections or sepsis caused by non-pancreaticobiliary disease
- Child-Pugh class B or C liver cirrhosis
- Females that are currently lactating

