### 11.2. Risks related to study medication

Treatment with PAMORA may be uncomfortable for patients as they may experience side effects like diarrhea or nausea. PAMORAs, especially methylnaltrexone, can worsen the clinical course of intestinal stenosis, because they increase motility and secretion in the intestine. At worst, this can cause perforation of the intestines which can be fatal. This has been accounted for in the exclusion criteria (see section 7.2.2.).

Participation in the study will be potentially beneficial for patients with AP receiving active medication and it is expected that this study will produce important knowledge on the treatment of AP for future patients. In

this regard, the use of placebo is crucial for evaluating the true effect of PAMORAs on the course of disease. Furthermore, all patients, regardless of whether they receive active treatment or placebo, may gain new insights and understanding into the pathophysiology of their disease and possible beneficial future treatment. The treatment of patients receiving placebo will not be affected by participation in the study as they still receive standard treatment.

In conclusion, the risk the participants are exposed to in this study is minimal compared to the beneficial information that will be gained from the study – both for the individual patient, but also for future treatment of patients with AP.

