4.1. Subject Disposition

Patients will be contacted by study personnel upon admission to be informed and potentially included in the study. Participation is complete voluntary, and consent can be revoked, should the participant wish to do so. Participants do not receive any economic compensation, but participation will be potentially beneficial for patients receiving active medication and it is expected that this study will produce important knowledge on the treatment of acute pancreatitis for future patients. Furthermore, all patients, regardless of whether they receive active treatment or placebo, may gain new insights and understanding into the pathophysiology of their disease and possible beneficial future treatment.

To identify patients at risk of moderate-to-severe disease, patients must fulfill two or more systemic inflammatory response syndrome (SIRS) criteria within the past 24 hours prior to inclusion. This assumption is based on previous findings that the fulfillment of two or more SIRS criteria is a good predictor of severity in patients with acute pancreatitis (18–20). In- and exclusion criteria are listed below:

Inclusion criteria

- Signed informed consent before any study specific procedures
- Able to read and understand Danish
- Age between 18 and 85 years
- The researcher believes that the participant understands what the study entails, is capable of following instructions, can attend when needed, and is expected to complete the study
- For fertile female participants: negative pregnancy test and use contraception during the study period.
- Within the current hospital admission and prior to inclusion, the patient must fulfill at least two of the following criteria to establish a diagnosis of AP (according to the revised Atlanta criteria (21): i) abdominal pain consistent with AP (acute onset of a persistent, severe, epigastric pain often radiating to the back); ii) serum amylase activity at least three times greater than the upper limit of normal; and iii) characteristic findings of AP on diagnostic imaging
- Predicted moderate or severe disease based on the fulfillment of 2 or more SIRS criteria

Exclusion criteria

- Definitive chronic pancreatitis according to the M-ANNHEIM criteria

- Known allergy towards study medication
- Known or suspected major stenosis obstruction or perforation of the intestines
- Toxic megacolon
- Known or suspected abdominal cancer (incl. intestine, pancreas and the biliary tree)

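### Protocol 11.2 says the exclusion criteria deal with the intestinal stenosis risk, but no line in 7.2.2 specifically excludes a known benign stenosis short of major obstruction, and SAP 4.1 words the line differently

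*Protocol*

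**What the plan says.** Protocol 11.2 states that drugs of this class, and methylnaltrexone in particular, "can worsen the clinical course of intestinal stenosis, because they increase motility and secretion in the intestine". It continues: "At worst, this can cause perforation of the intestines which can be fatal". It then states the mitigation: "This has been accounted for in the exclusion criteria", with a cross-reference to 7.2.2.

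Protocol 7.2.2 lists 11 exclusion criteria. The one closest to this risk is "Known or suspected major obstruction or perforation of the intestines". Two others concern the bowel: "Toxic megacolon", and a line on known or suspected abdominal cancer that includes the intestine. A further line excludes severe pre-existing comorbidities as assessed by the investigator.

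SAP 4.1 repeats the eligibility list. There the first of these lines reads "Known or suspected major stenosis obstruction or perforation of the intestines".

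**The concern.** Section 11.2 is part of the protocol's risk justification, and the section ends by calling the risk to participants minimal. For the one potentially fatal drug effect it describes, the only mitigation it gives is the pointer to 7.2.2. The reader who follows that pointer finds a criterion about major obstruction and perforation, not about the condition that 11.2 says the drug can worsen. The SAP, which should state the same population, has a different wording that does contain the word stenosis.

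What is at stake is patient safety at entry and agreement between the two documents. Someone applying 7.2.2 as written could enrol a patient with a known benign stenosis without breaching any specific criterion, although 11.2 tells the ethics committee and the agency that the criteria handle this risk.

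**Working it through.** The plan gives no figure on this point, so the check compares the texts.

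**1. Scope of the stated risk.** Section 11.2 speaks of intestinal stenosis without a grade or cause. It does not limit the risk to stenosis that is already obstructing or malignant.

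**2. Count of the criteria in 7.2.2.** There are 11 lines. Lines naming stenosis: 0. Lines about the bowel: 3 (major obstruction or perforation; toxic megacolon; abdominal cancer including the intestine). Exclusion lines left to the investigator's judgement: 1 (severe comorbidities).

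**3. Types of patient against the specific lines.**

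| Patient at screening | Specific line in 7.2.2 | Excluded by it? |
|---|---|---|
| Stenosis amounting to known or suspected major obstruction | Obstruction or perforation | Yes |
| Stenosis from known or suspected abdominal cancer | Abdominal cancer | Yes |
| Known or suspected perforation | Obstruction or perforation | Yes |
| Toxic megacolon | Toxic megacolon | Yes |
| Known or suspected benign stenosis, not a major obstruction | None | No |

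The gap is the last row only.

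**4. Whether the SAP wording closes the gap.** The SAP line seems to lack a comma or a conjunction after the word stenosis. It could mean major stenosis, obstruction or perforation as separate items, or an obstruction caused by a major stenosis. On either reading stenosis is qualified by major, so a lesser stenosis still passes. The SAP suggests that stenosis was in mind, but copying its text into the protocol would not make 11.2 hold.

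**5. What else could keep such a patient from exposure.**

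- Severe comorbidities (7.2.2): applies if the investigator regards the stenosis as severe. It does not mention the bowel.
- The researcher's expectation that the participant will complete the study (7.2.1): also a judgement, and also not about the bowel.
- Baseline CT (7.5.1 and 9.1.5; 11.1 places it upon admission and makes it available to the attending physicians): may show a stenosis. No text requires it to be read for stenosis before the first infusion, and no exclusion is tied to such a finding.
- Daily evaluation (7.5.1) and withdrawal for medical reasons (7.3.2): both act only after infusion has begun. The one medical condition that 7.3.2 names as a reason to stop treatment is renal impairment requiring dialysis.

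These safeguards are real, but each is general and depends on judgement. Section 11.2 attributes the protection to the exclusion criteria.

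**6. Effect on the statistics.** The sample size (protocol 7.6, SAP 3.1) rests on a difference of 25 points, a standard deviation of 40, 80% power and a two-sided alpha of 0.05. None of these, and nothing in the primary analysis, depends on this line.

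**The case against.** The strongest reply is that 11.2 says only that the risk was taken into account, not that every stenosis is excluded. The authors may have chosen to name the dangerous state, major obstruction or perforation, rather than the lesion behind it. Nothing in the documents shows that a mild benign stenosis carries the risk in 11.2; that follows only from the absence of a grade there. The SAP list also paraphrases the protocol elsewhere (it shortens the contraception and lactation lines, for example), so the extra word may be a typing slip or an effect of reading the PDF. Investigators also have several general means of keeping such a patient out. On this view the mismatch is editorial and could be cured by rewording 11.2.

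Much of this stands. The worst cases are already excluded, the SAP wording is weak evidence of intent, and the general safeguards should not be dismissed. What does not fall away is that 11.2 describes the drug as worsening a stenosis. A patient whose stenosis is not yet a major obstruction is therefore within the risk as described and outside the exclusion as written. Rewording 11.2 alone would make the documents agree but would leave that patient eligible.

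A reader might go further and infer that the trial admits patients with bowel obstruction unprotected, or that participants will be harmed. The documents support neither. Major obstruction, cancer-related stenosis and perforation are excluded, and no frequency is given for the remaining group.

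**Conclusion.** The point holds as a minor patient-safety and consistency issue. The entry rule does not fully deliver the mitigation that 11.2 claims: 0 of 11 exclusion lines name stenosis, and a known or suspected benign stenosis short of major obstruction is left to general, discretionary safeguards.

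Its size cannot be put in patients. The group is narrow by definition and may be empty, and any exposure percentage would rest on an invented count. The conclusion assumes that the ungraded wording in 11.2 means what it says and that the two eligibility lists are meant to describe one population. The product label, to which protocol 6.1.1 refers, was not available and is not relied on. It would be wrong to infer a threat to the trial's result: alpha, power, sample size and the primary analysis are unaffected.

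**What to change.** Change the line in protocol 7.2.2 to: *Known or suspected intestinal stenosis (including any seen on the baseline CT before first infusion), major obstruction, or perforation of the intestines.* Use identical text in SAP 4.1. The statement in 11.2 then holds as it stands. The new line leaves stenosis unqualified on purpose, since a term such as clinically relevant would bring back the same discretion as major.

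The cost is a protocol amendment. Under protocol section 11, a significant modification needs approval from both the regional ethics committee and the Danish Medicines Agency before it takes effect. A few candidates may be lost, and sites would need to have looked at the baseline CT before starting the infusion for the bracketed clause to work. No analysis changes.

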#### 7.3.4. Concomitant medication and care

Patients participating in the study will receive supportive treatment according to the IAP/APA evidence-based guidelines for the management of AP (2) as prescribed by the treatment-responsible physician. This includes supportive therapy with intravenous fluid therapy (Ringer's lactate 5-10 ml/kg per hour), enteral feeding (elemental or polymeric enteral nutrition formulations via nasojejunal or nasogastric route, alternatively parenteral if nasojejunal tube feeding is not tolerated) and analgesics. As the patients will be admitted during participation in the study, all concomitant medication and care will be registered in the patient's medical files as with any other patient and subsequently transferred to the CRF. This specifically includes a detailed quantification of the need for analgesics (separated into opioids and non-opioids) as this is of great clinical significance.

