#### 7.6. Sample size

We calculated that 41 patients per group will be needed to detect a difference in the PASS score of 25 points with a within-group standard deviation of 40 points (22), 80 % power and a 2-sided alfa level of 0.05. Hence, the sample size is set at 45 patients per group to allow for possible dropouts.

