### Pancreatitis activity scoring system

Clinical feature	Weight
Organ failure	100 per system
Intolerance to solid diet	0/40 (N/Y)
Systemic inflammatory response syndrome (SIRS)	25 per criteria
Abdominal pain	(0-10) x 5
Intravenous morphine equivalent dose (mg)	(1/mg) x 5

EXAMPLE: Patient with acute pancreatitis

Kidney failure, tolerant to solid diet, fulfills 1 SIRS criteria, scores abdominal pain 6, need of 20 mg intravenous morphine  
 $\text{PASS} = 100 + 0 + 25 + (6*5) + (20*5) = \underline{255}$

SIRS criteria
1. Body temperature $> 38^\circ\text{C}$ or $< 36^\circ\text{C}$
2. Heart rate $> 90/\text{min}$
3. Respiration $> 20/\text{min}$ or $\text{PaCO}_2 < 32\text{mmHg}$
4. White blood cell count $> 12.0 \times 10^9/\text{L}$ or $< 4.0 \times 10^9/\text{L}$

EXAMPLE: Patient with acute pancreatitis

Body temperature  $37.8^\circ\text{C}$ , Heart rate 120, Respiration 19/min  
White blood cell count  $18.0 \times 10^9/\text{L}$   
 $\text{SIRS score} = 0 + 1 + 0 + 1 = \underline{2}$

Figure 2: Pancreatitis Activity Scoring System (PASS)

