2.5.2. Secondary Endpoints

The secondary and exploratory endpoints are assessed at baseline, daily during treatment and at 14-day follow-up.

3. Study Design

This is a multicenter, investigator-initiated, double-blind, 1:1 randomized, placebo-controlled interventional, parallel-group, superiority trial, that will be conducted at four referral centers for acute pancreatitis in Denmark (Aalborg University Hospital, Odense University Hospital, Copenhagen University Hospital Hvidovre, and Bispebjerg Hospital). The Danish regulations have approved the trial: The North Denmark Region Committee on Health Research Ethics (Identifier: N-20200060) and the Danish Medicines Agency (EudraCT identifier: 2020-002313-18). We plan to prospectively include 90 patients admitted with predicted moderate-to-severe acute pancreatitis. Written informed consent will be obtained from all participants prior to any trial-specific procedures. Patients entering the study, will be randomized 1:1 to receive 5 days of intravenous methylnaltrexone or matching placebo, during admission. While participating in the study, patients will receive standard treatment according to guidelines and no concomitant medication is prohibited. After discharge patients will be invited to complete a 14-day follow. In addition to treatment with PAMORA, patients will undergo a series of examinations daily during treatment and at the 14-day follow-up, according to figure 2.

[figure not shown]

Figure 2

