3.1. Sample Size

We calculated that 41 patients per group will be needed to detect a difference in the PASS score of 25 points with a within-group standard deviation of 40 points (9), 80 % power and a 2-sided alfa level of 0.05. Hence, the sample size is set at 45 patients per group to allow for possible dropouts.

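### A habitual opioid dose is scored as pancreatitis activity in the primary PASS endpoint; this adds noise, not bias, and the 48-hour analysis should account for it

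*Protocol*

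**What the plan says.** **Eligibility.** Neither Protocol 7.2.1–7.2.2 nor SAP 4.1 mentions long-term opioid therapy or opioid substitution. The one discretionary item is "Severe pre-existing comorbidities (assessed by investigator upon inclusion". SAP section 3 adds that "no concomitant medication is prohibited".

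**Score.** In the PASS table (Protocol 9.1.1, Figure 2; SAP 2.1, Figure 1) the item "Intravenous morphine equivalent dose (mg" carries 5 points per mg. No cap, deduction, conversion rule or dose window is given. The documents' own example turns 20 mg into 100 points, the weight of one failed organ system.

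**Recording.** Protocol 7.3.4 says of care during admission: "This specifically includes a detailed quantification of the need for analgesics (separated into opioids and non-opioids". No section requires the pre-admission dose. It is not among the descriptive variables in SAP 2.4, and SAP 3.2 randomizes without stratification.

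**Design.** Protocol 7.6 plans to "detect a difference in the PASS score of 25 points with a within-group standard deviation of 40 points", with "80 % power and a 2-sided alfa level of 0.05".

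**Analysis.** Protocol 9.3 specifies a mixed model with treatment, time and their interaction, and no baseline covariate. SAP 6.1 adds baseline PASS to that model. It then assesses the 48-hour difference with a post-hoc Bonferroni-corrected t-test, or Mann-Whitney if Shapiro-Wilk rejects normality, and states no covariate for that step.

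**The concern.** A dose that a patient took before the attack says nothing about the severity of the attack or about the treatment. If it continues in hospital and is scored, it adds a fixed block of points at each inpatient assessment. The 25-point target equals 25 / 5 = 5 mg, and the planning SD of 40 equals 40 / 5 = 8 mg, so even a modest habitual dose exceeds both within that patient's score. A small subgroup with such doses widens the distribution of 48-hour PASS and gives it a heavy upper tail, which costs power in a trial of 45 per arm. Because the pre-admission dose is not collected, the problem could later be examined only by going back to the charts.

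**Working it through.** **Inputs from the documents:** difference 25, SD 40, two-sided alpha 0.05, 80% power, 41 per group raised to 45 (Protocol 7.6, SAP 3.1); 5 points per mg (PASS table).

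**Inputs assumed:** share p of long-term users 2–10%; habitual dose D 20–60 mg of intravenous morphine equivalent, constant from baseline to 48 hours; SD 40 for PASS without the habitual dose; baseline-to-48-hour correlation r of the remaining score 0.3 or 0.5.

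**The plan's own figure.** n = 2 × (1.960 + 0.842)² × 40² / 25² = 40.2, so 41 per group. It reproduces. With 45 per arm, power is 84%.

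**Effect on one score.** 5 × 20 = 100 points, four times the target.

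**Effect on an arm mean.** Shift per excess user = 5D / 45:
- 20 mg: 100 / 45 = 2.2 points, so a 25-point shift needs 25 / 2.2, about 11 excess users.
- 60 mg: 300 / 45 = 6.7 points, so it needs 25 / 6.7, about 4 excess users.

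With 45 per arm, the chance of an imbalance of 4 or more is 1% if p = 2%, 9% if p = 5% and 21% if p = 10%. An imbalance of 11 or more has a chance of at most about 0.03%.

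**Effect on spread.** SD = √(40² + p(1 − p)(5D)²). For p = 5% and D = 20: √(1600 + 0.0475 × 10,000) = 45.6. For p = 10% and D = 60: √(1600 + 0.09 × 90,000) = 98.5.

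**Simulated power** (45 per arm, true difference 25, alpha 0.05). The SAP rule is the t-test if Shapiro-Wilk passes in both arms, otherwise Mann-Whitney. The last column is analysis of covariance on baseline PASS, for r = 0.3 to 0.5.

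| Share, dose | SD | Plain t-test | SAP 6.1 rule | Adjusted for baseline PASS |
|---|---|---|---|---|
| none | 40 | 84% | 84% | 87–91% |
| 2%, 60 mg | 58.0 | 56% | 79% | 78–88% |
| 5%, 20 mg | 45.6 | 74% | 75% | 82–90% |
| 5%, 60 mg | 76.6 | 36% | 74% | 75–86% |
| 10%, 20 mg | 50.0 | 65% | 68% | 80–90% |
| 10%, 60 mg | 98.5 | 24% | 63% | 72–85% |

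Repeat runs move individual entries by a few points; 71–90% is a fair overall range for the last column with users present. With no true difference, rejection stays near 5% throughout. Where r is only 0.3 and 2% or 5% of patients take 60 mg, adjustment does no better than the rank test: one common slope cannot fit both a constant habitual dose and a weakly correlated acute score.

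**Effect of scoring only the excess.** For 5% of patients at 40 mg, power is 52–53% (t-test), about 73% (Mann-Whitney), 76–87% (baseline-adjusted), and 86–91% when only opioid above the habitual dose is scored, also with baseline adjustment. The last is about the level with no such patients.

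The simulation leaves out the requirement that the mixed model first be significant, and the Bonferroni correction. It therefore compares 48-hour tests and does not give the full power of SAP 6.1.

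**The case against.** A reader might infer that a few long-term users could overwhelm the 25-point target or bias the result. The arithmetic does not support that. About 4 excess users at 60 mg, or 11 at 20 mg, are needed to move the mean difference by 25 points. Randomization makes any imbalance a matter of chance, and type I error holds. The Mann-Whitney fallback also protects: at 5% and 60 mg it lifts power from 36% to 74%, so the inflated SD does not describe the test that would be used. These points stand, and they limit the concern to power.

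Baseline PASS is already in the SAP's mixed model, and a constant dose sits in both the baseline and the 48-hour scores. This stands in part: SAP 6.1 does not carry the adjustment into the 48-hour test, and adjustment leaves some loss.

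The inputs are missing. The documents give neither the share nor the doses of long-term users, nor whether the cited SD of 40 already includes them. If it does, adding their variance counts it twice. SAP section 5 also describes the opioid item as need for opioid treatment, which could be read as need for this attack only; that the habitual dose is scored follows from the absence of any deduction. Definitive chronic pancreatitis and abdominal cancer, both plausible sources of such patients, are already excluded.

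A reader might also conclude that long-term users must be excluded, or that they bring in a second indication because the drug is "approved and sold on the Danish marked for treatment of opioid-induced constipation". In a trial of opioid antagonism, excluding them is a debatable trade-off. The second point is unquantified and mainly concerns gut outcomes that SAP 2.3 calls exploratory.

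**Conclusion.** The point holds as a matter of precision. Long-term opioid users are eligible, PASS as written scores their habitual dose as disease activity, and the dose needed to separate the two is not collected. Under the assumed shares and doses, the unadjusted 48-hour comparison loses about 5 to 21 percentage points of power (84% to 63–79%). A baseline-adjusted contrast recovers much but not all of the loss. The range rests on shares of 2–10%, doses of 20–60 mg, a constant dose and an SD of 40 that excludes such patients, none of which the documents settle. If the SD of 40 already includes them, the loss against the planned 80% is smaller or absent, although excess-only scoring would still sharpen the comparison. The documents show neither bias nor a defect in the eligibility list that has to be corrected.

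**What to change.** 1. Record each patient's pre-admission opioid dose at baseline, in intravenous morphine equivalents and from the medical records, and add it to the descriptive variables in SAP 2.4. State the conversion rule and the time window for the PASS opioid item, so that the two doses are on the same scale.
2. In SAP 6.1, take the 48-hour treatment contrast from the mixed model with baseline PASS as covariate, in place of the separate t-test or Mann-Whitney test, and align Protocol 9.3.
3. Pre-specify a sensitivity analysis of 48-hour PASS that counts only opioid above the pre-admission dose. The primary score stays as published.

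The cost is one data item, one extra analysis and a wording change, all to be settled before unblinding. Excluding long-term users remains an option for the sponsor, at the price of narrower generalisability, but it is not needed to resolve this point.
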